APPENDIX A: Screening Questionnaire

Screening Questionnaire

Script [read to all travelers]: Hello, my name is [name] and I am a [role in the clinic] at The New York Center for Travel and Tropical Medicine. We are conducting a study of international travelers to see if bismuth subsalicylate (or BSS) can help to prevent travelers' diarrhea. Participation in this questionnaire to see if you are eligible is voluntary, and it will only take a moment of your time. We will be collecting your email address, so in the event that you are eligible to participate, we can send you the study questionnaires and reminder emails; your email will only be used for study purposes. Are you interested in seeing if you are eligible to participate?

YES NO

[If "yes", please complete the following with the traveler]:

Participant's Initials		Date	
Age			

Participant Email (REQUIRED): _____
 Participant Phone #1 (OPTIONAL): _____ Participant Phone #2 (OPTIONAL): _____

1. Are you ≥ 18 years of age and <70 years of age?

Yes* No Don't know

2. Are you traveling to either South East Asia, South Central Asia, North Africa, or Sub-Saharan Africa?

Yes* No Don't know

3. Are you spending at least 7 days and no more than 21 days in these regions?

Yes* No Don't know

4. Are you leaving for your trip in at least 7 days?

Yes* No Don't know

5. Are you now pregnant or nursing or do you plan to get pregnant before the end of your trip?

Yes No* Don't know

6. Do you have known or suspected allergy to bismuth, salicylate, or aspirin?

Yes

No*

Don't know

7. Do you have known or suspected allergy to microcrystal cellulose, calcium carbonate, artificial coloring, magnesium, mannitol, povidone, saccharin, or talc?

Yes

No*

Don't know

8. Do you have kidney disease, diabetes, gout, or a clotting disorder?

Yes

No*

Don't know

9. Have you taken an antibiotic in the past 30 days? For example:

- Doxycycline or minocycline
- Flagyl, cotrimoxazole (e.g., Bactrim, Septra)
- Penicillins (e.g., amoxicillin, Augmentin)
- Cephalosporins (e.g., Keflex)
- Fluoroquinolones (e.g., ciprofloxacin)
- Macrolides (e.g., azithromycin [Zithromax], erythromycin)

Yes

No*

Don't know

10. Do you take any of the following medications or therapies?

- Chronic oral or intravenous IV steroids (e.g., hydrocortisone or prednisone); not inhaled steroids
- Alkylating agents (e.g., cyclophosphamide [Cytoxan])
- Antimetabolites (e.g., azathioprine [Imuran], 6-mercaptopurine [Purinethol])
- Chemotherapeutic agents (e.g., including methotrexate [Trexall])
- Tumor necrosis factor (TNF) blockers (e.g., etanercept [Enbrel], adalimumab [Humira], certolizumabpegol [Entyvio], golimumab [Simponi], and infliximab [Remicade])
- Monoclonal antibodies (e.g., rituximab [Rituxan] or alemtuzumab [Lemtrada])
- Insulin (e.g., Humalog, NPH, Lantus, Levemir)
- Valproic acid (e.g., divalproex, Depakote, Depacon)
- ACE-inhibitors (e.g., lisinopril [Zestril], enalapril [Vasotec], captopril [Capoten], ramipril [Altase], benazepril [Lotensin])
- Anticoagulants (e.g., warfarin [Coumadin], aspirin, clopidogrel [Plavix], argatroban [Acova], bivalirudin [Angiomax], dabigatran [Pradaxa])

Yes

No*

Don't know

11. Do you have any of the following chronic stomach or intestinal illnesses?

- Irritable bowel syndrome (IBS)
- Inflammatory bowel disease (including ulcerative colitis and Crohn's disease)
- Celiac disease; any form of chronic diarrhea or chronic abdominal pain;
- Pancreatic insufficiency
- Gallbladder disease
- Malabsorption syndromes
- Gastrointestinal malignancy/cancer currently receiving chemo; radio, or immunotherapy
- Chronic diarrhea from another cause

Yes No* Don't know**12. Do you have any illnesses that you have been told lowers your body's ability to fight infection?**

- Missing or non-functioning spleen
- Insulin-dependent diabetes mellitus
- Diabetes mellitus receiving oral hypoglycemic medications (e.g. metformin, glyburide)
- HIV/AIDS
- Other immunodeficiency syndrome (e.g. complement deficiency, antibody or immunoglobulin deficiency)
- Malignancy or cancer under active chemo, radio, or immunotherapy; or any other immunocompromising condition?

 Yes No* Don't know**13. Have you ever received a solid organ transplant?** Yes No* Don't know**14. Have you had diarrhea (3 or more unformed stools in 24 hours) in the 30 days before enrollment or do you currently have diarrhea?** Yes No* Don't know

*Must answer "Yes" to questions 1, 2, 3, AND 4 and "No" to all subsequent to be eligible for enrollment.

 Eligible per Appx A Not Eligible per Appx A

Comments:

By signing below, I confirm that I conducted the verbal screening and have reviewed the answers before proceeding with additional study activities:

Name of Interviewer		Signature	
Date			

If eligible, collect the following:

Participant First Name: _____ Participant Last Name: _____

State of Residence: _____ County of Residence: _____

Residence Zip Code: _____

Generation of Study ID and Group ID:

UNIQUE STUDY ID:

The unique study ID will include a site letter designation of "T", year, and participant number (provided numerically from 1 to 10,000).

*For example, the unique identifier for the first participant would be: T2017-00001.

GROUP ID:

The group ID will begin with "G" and a group number (provided numerically from 1 to 10,000). Those participants who are travel companions and have identical itineraries to other participants in the study

and anticipate performing the same activities, (including family and friends), are given the same number.

*For example, the group ID for the first participant would be G-00001. Their mother, traveling with them, would also be G-00001.

Study ID Number	
------------------------	--

APPENDIX B: Country Listing for Inclusion

South East Asia

Cambodia
Laos
West Malaysia (excluding Malaysian Borneo)
Myanmar (Burma)
Thailand
Vietnam

South Central Asia

Afghanistan
Bangladesh
Bhutan
India
Maldives
Nepal
Pakistan
Sri Lanka

North Africa

Algeria
Egypt
Libya
Morocco
Sudan
Tunisia

Sub-Saharan Africa (*Does NOT include the country of SOUTH AFRICA*)

Angola	Congo	Guinea-Bissou	Mozambique	Sierra Leone
Benin	Democratic Republic of the Congo	Kenya	Namibia	Somalia
Botswana	Côte d' Ivoire	Lesotho	Niger	South Sudan
Burkina Faso	Djibouti	Liberia	Nigeria	Swaziland
Burundi	Equatorial Guinea	Madagascar	Reunion	United Republic of Tanzania
Cameroon	Eritrea	Malawi	Rwanda	The Gambia
Cabo (Cape) Verde	Ethiopia	Mali	Saint Helena	Togo
Central African Republic	Gabon	Mauritania	São Tomé and Príncipe	Uganda
Chad	Ghana	Mauritius	Senegal	Zambia
Comoros	Guinea	Mayotte	Seychelles	Zimbabwe

APPENDIX C: Pre-travel Questionnaire

Pre-travel Questionnaire

PARTICIPANT UNIQUE ID: _____

GROUP ID: _____

[Please review the screening questionnaire with the participant.]

Have there been any changes to the screening questionnaire making the participant ineligible to participate?

- a. Yes
- b. No

If yes, please describe:

Demographics

Age (in years): _____

Sex (M/F): _____

Race:

- a. White or Caucasian
- b. Black or African American
- c. American Indian or Alaskan native
- d. Asian or Pacific Islander
- e. Other (please specify) _____
- f. Don't know
- g. I would rather not answer

Ethnicity:

- a. Hispanic
- b. Non-Hispanic

Medical History

2. Do you have any medical conditions or illnesses?

- a. Yes
- b. No
- c. Don't know
- d. I would rather not answer

If yes to question 1, please list them all.

3. Do you have recurrent or persistent tinnitus (ringing in the ears)?

- a. Yes
- b. No
- c. Don't know
- d. I would rather not answer

4. Do you take any medications on a regular basis?

- a. Yes
- b. No
- c. Don't know
- d. I would rather not answer

If Yes to question 3, please list them all:

1.	4.
2.	5.
3.	6.

5. Have you taken any oral or intravenous (IV) antibiotics in the past 90 days for any reason (e.g., azithromycin [Zithro-max], ciprofloxacin [Cipro], rifaximin [Xifaxan], doxycycline or minocycline, metronidazole [Flagyl], cotrimoxazole [Bactrim or Septra], penicillins [e.g., amoxicillin or Augmentin], or cephalosporins [e.g., Keflex])?

- a. Yes
- b. No
- c. Don't know
- d. I would rather not answer

If yes to question 4, please give the antibiotic name, start date, duration, and illness taken for:

No.	Antibiotic Name	Start Date (MM/DD/YYYY)	Duration (Days)	Illness taken for
1				
2				
3				
4				
5				
6				

6. In the past 30 days, have you taken a probiotic? -

Probiotics are live microorganisms (such as certain types of bacteria) that may benefit the health of the person consuming them. Yogurts and other fermented dairy products are probiotics. Probiotics can also take the form of capsules, pills, or powders. Probiotics also include any foods or drinks labeled as containing "live and active cultures" or "probiotics."

- a. Yes

- b. No
- c. Don't know
- d. I would rather not answer

Travel History

7. Have you traveled internationally in the past 90 days?

- a. Yes
- b. No
- c. Don't know
- d. I would rather not answer

If yes to question 6, which countries did you travel to and what were your dates of travel? If the exact dates of travel are unknown, please list the month and year only.

Country name	Dates of travel (MM/DD/YY to MM/DD/YY)
1.	__/__/__ to __/__/__  Unknown
2.	__/__/__ to __/__/__  Unknown
3.	__/__/__ to __/__/__  Unknown
4.	__/__/__ to __/__/__  Unknown
5.	__/__/__ to __/__/__  Unknown
6.	__/__/__ to __/__/__  Unknown

8. Where are you planning to travel? Please specify each country name, the specific locations you plan to visit, and the number of days you plan to spend in each country.

Country name	Specific location(s) to be visited (e.g., city/town, attraction)	Number of days in this country
1.		
2.		
3.		

4.		
5.		
6.		

9. What is the total duration of your trip (in days)?

10. What is your main reason for travel (circle only one)?

- a. Education or research (includes medical or veterinary-type education)
- b. Adoption
- c. Business
- d. Leisure/tourism
- e. Immigrant traveling back to visit friends or relatives
- f. Providing medical care as a health professional (including paid or unpaid/volunteer)
- g. Receiving medical care (as a patient)
- h. Non-medical service or volunteer work
- i. Missionary work
- j. Military service
- k. Attending large gathering or event (e.g., large sporting event, large conference, Hajj)
- l. Adventuring (extreme mountaineering, water sports, outdoor activities, etc.)
- m. Other:

- n. I would rather not answer

11. What are the secondary reasons for travel (circle all that apply)?

- a. Education or research (includes medical or veterinary-type education)
- b. Adoption
- c. Business
- d. Leisure/tourism
- e. Returning to region of origin of self or family to visit friends and relatives
- f. Providing medical care as a health professional (including paid or unpaid/volunteer)
- g. Receiving medical care (as a patient)
- h. Non-medical service or volunteer work
- i. Missionary work
- j. Military service
- k. Attending large gathering or event (e.g., large sporting event, large conference, Hajj)
- l. Adventuring (extreme mountaineering, water sports, outdoor activities, etc.)
- m. Other:

- n. I would rather not answer

This survey is now completed.

Thank you very much for your time.

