9. Have had diarrhea (see Definitions) anytime in the previous 30 days, have diarrhea at the pre-travel consultation, or develop diarrhea before departure
10. Have been given doxycycline for malaria prophylaxis for the current trip (due to possible drug-drug interactions and decreased absorption of the doxycycline) (27)
11. Have an allergy to any component of the placebo tablets

Estimated Number of Participants

We anticipate enrolling approximately 500 participants (see Sample Size and Power Calculation).

Sample Size and Power Calculation

A sample size of 488 participants with full compliance to medications and questionnaires (244 participants in each arm) is needed to fulfill the objectives [anticipated incidence of the endpoint as 40% incidence of TD with a 30% minimum intervention protection ($0.40-[0.4 \times 0.30] = 0.28$) with an alpha of 0.05, and 80% power].

Recruitment and Enrollment

All international travelers undergo a screening questionnaire at their pre-travel consultation to determine eligibility. This short questionnaire includes questions regarding the travelers' [see **APPENDIX A**]:

1. Age
2. Travel destination(s)
3. Trip duration
4. Acute and chronic medical conditions, including diarrhea
5. Contraindications to BSS administration
6. All current medications, including antibiotic use within the 30 days before screening
7. Willingness to participate in the trial and comply with the data collection requirements

This screening questionnaire will be administered to the traveler by study personnel at The New York Center for Travel and Tropical Medicine. The purpose will be to exclude those travelers who do not meet all inclusion criteria and those who meet any exclusion criteria (see Participant Inclusion / Exclusion Criteria). Travelers who meet the inclusion criteria and do not meet any exclusion criteria will be introduced to the project objectives and procedures, including the procedures for biologic (stool) specimen collection (see Laboratory instruments).

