Participants will be provided two OMNIgene gut kits at their pre-travel consultation/enrollment visit once enrolled (see Biologic [Stool] Specimen Data Collection and Testing). These kits will come with instructions on use, handling, and shipment.

In the event that participants are able to provide a stool sample while in clinic for their pre-travel consultation/enrollment visit or during a non-study post-travel follow-up sick visit within 10 days of return, these samples will be aliquoted by study personnel at The New York Center for Travel and Tropical Medicine in the following manner:

*First, the required quantity will be placed in the participant's OMNIgene gut kit (per manufacturer directions) to be sent to CDC's Clinical and Environmental Microbiology Branch for resistome testing. The remainder will be frozen, and sent to CDC for analysis at a later date (note: OMNIgene gut kit does not allow for culture - a see Biologic [Stool] Specimen Collection and Testing). Only those participants who happen to have a biologic (stool) specimen collection completed at the clinic will have their stool analyzed by culture; this is not a requirement for participation and no additional compensation above that previously described will be offered.

Table 3. Schedule of LABORATORY events (secondary objective)

(Events from Table 2 still apply to these participants)

	Stages		
	Pre-travel	During travel	Post-travel
Biologic (stool) sample	X		X
Laboratory testing of stool	X		X

Analytic tests

Questionnaires: Data from the questionnaires will be analyzed for statistical significance comparing intervention vs placebo groups.

Biologic (stool) specimens: A highly multiplexed PCR assay detecting over 500 different AMR genes will be used to test the DNA extracted from all biologic (stool) specimens that were placed in the OMNIgene gut kit (see Biologic (Stool) Specimen Collection and Testing). Results will be analyzed to determine if the participants acquire gut AMR genes (changes to the “resistome”) as a result of travel and whether or not that change varied with the bismuth subsalicylate treatment received. Additionally, stool bacteriologic culture will be performed on those specimens submitted in clinic.

Intervention

We propose the inclusion of two arms to test BSS against placebo:

1. BSS 4 tablets po bid (2.1 grams total)
2. Placebo 4 tablets po bid

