Additionally, an incident report will be filed as required by the reviewing IRB if there is an unexpected violation of study procedures or expectations or if unanticipated problems or adverse events are identified.

If deemed necessary by the IRB, we would consider using a Study Data Safety Monitoring Board to analyze the data and stop the study early in the event there are serious adverse outcomes that are significantly higher in the placebo or intervention arm. However, due to the relative safety of BSS, we do not anticipate this will be necessary.

Due to the number of participants that will need to be enrolled in this study to achieve adequate power, there is the possibility that this study may extend beyond the current study timeline. Although we do not anticipate difficulty enrolling participants, we want be prepared for any unanticipated issues with enrollment. In the event that 488 participants are not enrolled at two years, an interim analysis will be performed and additional funding will be requested to continue the project until adequate power is achieved.

Identifying, Managing, and Reporting Adverse Events

Adverse events in this study may include, but are not limited to, the following:

1. Medication side effects, such as constipation, tinnitus, or dizziness
2. Medication adverse events, such as neurologic findings from salicylate toxicity (confusion, slurred speech, drowsiness, muscle weakness, headache, mental depression) or severe stomach pain, increased sweating, or increased thirst

All participants will be asked about adverse events on each of the study questionnaires, including the daily questionnaire while traveling. If the participant experiences an

adverse event while abroad, they are to stop the study medication and contact the study personnel to report the symptoms and obtain advice.

Notifying Participants of their Individual Results

Participants will not be notified of their study results, since the results will not impact their healthcare.

Disseminating Information to the Public

The results from this study will be published in a peer-reviewed journal, however, the initial release may be in the form of an abstract for a scientific meeting.

Preliminary study findings will be shared with P&G after the data analysis phase is complete.

Budget Estimates

Table 4. CLINIC events with estimated costs (primary objective)

NOTE: Table 4 costs are for 500 participants

	Stages			

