APPENDIX D: During-travel Questionnaire

During Travel Questionnaire

PARTICIPANT UNIQUE ID: _____

GROUP ID: _____

	Day 1	Day 2	Day 3	Day 4	Day 5
Please write the calendar date that corresponds to each day of your trip. Day 1 is your first day of arrival in the country.					
Number of tablets taken in the morning (maximum 4)					
Number of tablets taken in the afternoon/evening (maximum 4)					
Symptoms in the prior 24 hours (check off all that apply)	... 				
Fever					
Nausea					
Vomiting					
Loose stools (less than three in a 24 hour period)					
Diarrhea (three or more loose stools in 24 hours)					
Bloody diarrhea					
Constipation					
Dark or black stool					
Dark or black tongue					
Abdominal pain					
Abdominal cramps					
Urgency to relieve oneself (in reference to stool)					
Bloating					
Flatulence/gas					
Congestion/runny nose					
Sore throat					
Cough					
Rash					
Headache					
Dizziness					
Ringing in your ears					
Muscle pain/soreness					
Joint pain/swelling/redness					

Drowsiness (severe)					
Confusion					
Depression					
Other (list/describe):					
Medical care
Did you seek medical care for one or more of these symptoms? (Yes/No/Don't Know)	Y N D	Y N D	Y N D	Y N D	Y N D
→ If yes, where? (check the corresponding box(es))
A doctor's office					
Urgent care clinic (outpatient)					
Emergency room					
Hospital outpatient clinic setting					
Hospital inpatient ward – hospitalized					
Other (specify)					
→ Was your diagnosis travelers' diarrhea? (Yes/No/Don't Know)	Y N D	Y N D	Y N D	Y N D	Y N D
Have you started any medications in the past 24 hours? (Yes/No/Don't Know)	Y N D	Y N D	Y N D	Y N D	Y N D
→ If yes, what medication(s)?					
→ Please circle those that were provided for you at your pre-travel consultation with the study clinic.

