- b. **Antidiarrheals** (e.g., bismuth subsalicylate [Pepto Bismol/Kaopectate])
- c. **Antimotility agents** (e.g., loperamide [Imodium])
- d. **H2 blocker** (e.g., ranitidine [Zantac], cimetidine [Tagamet], famotidine [Pepcid])
- e. **Proton pump inhibitor** (e.g., omeprazole [Prilosec], pantoprazole [Protonix], lansoprazole [Prevacid], esomeprazole [Nexium])
- f. **Other antacids** (e.g., calcium carbonate [Tums/Rolaids], Maalox/Mylanta)
- g. **Probiotics** (*Yogurts and other fermented dairy products are probiotics. Probiotics can also take the form of capsules, pills, or powders. Probiotics also include any foods or drinks labeled as containing "live and active cultures" or "probiotics"*)
- h. **Oral or intravenous steroids** (e.g., prednisone, hydrocortisone)
- i. **Local/natural or herbal remedies** (herbs, etc.)
- j. **Other:**

3. Did you experience any of the following at any point during your travels?

Symptom	(Yes/No/Don't Know)	If yes, what was the duration (in days)?
Ringing in your ears	Y N D	
Constipation	Y N D	
Dark or black stool	Y N D	
Dark or black tongue	Y N D	
Drowsiness	Y N D	
Nausea	Y N D	
Vomiting	Y N D	
Rash	Y N D	
Other (list/describe):		

4. Did you seek medical care for an illness since returning to the United States after your trip?

- a. Yes
- b. No
- c. Don't know
- d. I would rather not answer

If yes to question 4, where did you seek and receive care?

- a. A doctor's office
- b. Urgent care clinic (outpatient)
- c. Emergency room
- d. Hospital outpatient clinical setting
- e. Hospital inpatient ward – hospitalized
- f. Other (please specify)

If yes to question 4, what was/were your diagnosis/es?

If yes to question 4, were you told that your illness was related to travel?

- a. Yes
- b. No
- c. Don't know
- d. I would rather not answer

If yes to question 4, were you told that you had travelers' diarrhea?

- a. Yes
- b. No
- c. Don't know
- d. I would rather not answer

If yes to question 4, were you told that you had a bacteria that was resistant to antibiotics?

- a. Yes
- b. No
- c. Don't know
- d. I would rather not answer

5. Did you travel to any countries not discussed during your pre-travel visit?

- a. Yes
- b. No
- c. Don't know
- d. I would rather not answer

If yes to question 5, please list the new countries you visited, the location(s) visited, and the number of days in each country:

Country name	Specific location(s) to be visited (e.g., city/town, attraction)	Number of days in this country
1.		
2.		
3.		

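### Tinnitus present before travel is recorded but not separated from ringing reported on study tablets, which dilutes the arm comparison for a named side effect

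*Combined protocol and SAP*

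**What the plan says.** Appendix C, item 3 of the medical history, asks before departure: "Do you have recurrent or persistent tinnitus (ringing in the ears". The possible answers are Yes, No, Don't know, and a preference not to answer. Tinnitus is not among the exclusion criteria and the Appendix A screener does not ask about it, so travelers who have it can be enrolled. The only stated use of item 3 is the tinnitus row under medical history in the baseline table shell (Appendix I, Table 1).

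During travel, each daily column of Appendix D has a tick box for "Ringing in your ears". After travel, Appendix E lists the same symptom among those since returning home and again under the question "Did you experience any of the following at any point during your travels". None of these items asks whether the ringing is new or worse than before the trip.

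The section on identifying and reporting adverse events names tinnitus: "Medication side effects, such as constipation, tinnitus, or dizziness". The Outcomes table counts side effects of the intervention drug as a non-favorable outcome under Hypothesis 1. The only analysis statement that reaches these symptoms is under Analytic tests: "Data from the questionnaires will be analyzed for statistical significance comparing intervention vs placebo groups". Appendix I has no adverse-event table shell, and no section defines new-onset tinnitus.

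**The concern.** Item 3 is the only clean pre-dose record of tinnitus. The Intervention section starts dosing on the flight before arrival, and diary Day 1 is the day of arrival, so the diary has no pre-dose day. If every ringing report is compared by arm, a participant whose ears rang before the trip can be counted as a case whichever tablets they took.

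Randomization makes such participants equally frequent in the two arms on average. They add similar numbers of events to both sides, shrink the risk ratio and raise the variance. The error runs one way: a real drug effect is more likely to be read as no difference. This matters for a preventive product taken by healthy travelers, in a study meant to inform pre-travel advice. The variable that would remove the problem is already collected.

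**Working it through.** **The plan's own figure.** The Sample Size section gives "anticipated incidence of the endpoint as 40% incidence of TD with a 30% minimum intervention protection" and "with an alpha of 0.05, and 80% power", that is 0.40 versus 0.28. With two-sided alpha 0.05 and pooled null variance:

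n = [1.96·√(2 × 0.34 × 0.66) + 0.842·√(0.40 × 0.60 + 0.28 × 0.72)]² / 0.12² = 243.4, rounded up to 244 per arm.

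This matches "A sample size of 488 participants with full compliance to medications and questionnaires (244 participants in each arm"). Power at 244 per arm is 80.1%. The figure concerns TD only and is unaffected by this point. The documents give no rate, target difference or power for tinnitus.

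**Inputs for tinnitus.** From the documents: about 500 enrolled in equal arms, so 250 per arm. Assumed, because the documents are silent: b, the share with baseline tinnitus (2%, 5%, 10%), equal in both arms; q0 and q1, the risks of new tinnitus on placebo and bismuth subsalicylate (BSS) (1% versus 5%, or 2% versus 8%).

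**Formulas.**
- Everyone counted, all baseline cases ticking ringing: p = b + (1 − b)q in each arm, n = 250.
- Restricted to those without baseline tinnitus: q0 versus q1, n = 250(1 − b).
- Power = Φ[(|p1 − p0| − 1.96·SE0)/SE1], where SE0 is the pooled and SE1 the unpooled standard error.

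**Worked case: b = 5%, 1% versus 5%.**
- Everyone: p0 = 0.05 + 0.95 × 0.01 = 0.0595 and p1 = 0.05 + 0.95 × 0.05 = 0.0975. The difference is 0.038 and the risk ratio 1.64, against a true 5.0. SE0 = 0.02406 and SE1 = 0.02400. (0.038 − 1.96 × 0.02406)/0.02400 = −0.38, so power is 35%.
- Restricted: n = 237.5, SE0 = 0.01565, SE1 = 0.01555. (0.04 − 1.96 × 0.01565)/0.01555 = 0.60, so power is 73%.

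**Results, all baseline cases ticking.**

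| New tinnitus | b | Observed risk ratio | Power, everyone | Power, restricted | Relative loss |
|---|---|---|---|---|---|
| 1% vs 5% | 2% | 2.32 | 53% | 74% | 29% |
| 1% vs 5% | 5% | 1.64 | 35% | 73% | 52% |
| 1% vs 5% | 10% | 1.33 | 23% | 70% | 68% |
| 2% vs 8% | 2% | 2.48 | 74% | 86% | 15% |
| 2% vs 8% | 5% | 1.83 | 58% | 85% | 33% |
| 2% vs 8% | 10% | 1.46 | 40% | 83% | 52% |

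The risk difference is only multiplied by (1 − b). Most of the lost power comes from added variance.

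**Only half of the baseline cases ticking, 1% versus 5%.** Power with everyone counted is 47% to 49% at b = 5% and 33% to 35% at b = 10%. The lower value assumes that the other half never report ringing: p = b/2 + (1 − b)q. The upper value assumes that they share the new-onset risk: p = b/2 + (1 − b/2)q.

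**Check on the approximation.** Event counts are small, so Fisher's exact test was also tried at 244 per arm for 1% versus 5%. Power is 29% versus 65% at b = 5% and 18% versus 62% at b = 10%. The levels are lower, but the contrast is the same.

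**The case against.** A reader might infer that the tinnitus comparison loses most of its power. The documents do not support that. They state no tinnitus rates, no tinnitus hypothesis and no tinnitus power, so there is no planned power to lose. The relative loss in the table runs from 15% to 68%, and it passes one half only when baseline tinnitus is common relative to the new-onset risk. Item 3 covers recurrent as well as persistent tinnitus, and recurrent tinnitus need not appear during a trip of 7 to 21 days, so the all-tick case is the worst one.

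A reader might also infer bias between the arms. Randomization balances baseline tinnitus on average, so the effect is dilution and imprecision.

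It can fairly be said that the plan nowhere defines a tinnitus case. The sentence under Analytic tests is generic and does not order the pooling of participants with and without baseline tinnitus. Tinnitus is better served than constipation or dizziness, which have no baseline item of their own. The forms share the participant's unique ID, so the separation can still be made at analysis.

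All of this limits the size and severity of the point. It does not remove it. A rule chosen after the arms are known carries less weight than one written beforehand, and worsening among those with baseline tinnitus cannot be recovered from the present forms.

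**Conclusion.** The point stands as a minor gap in the safety analysis. No rule in the plan separates pre-existing from new tinnitus, and a comparison of all reported ringing would be diluted toward no difference. The restricted analysis had more power in every case in the table, even at 2% baseline prevalence, so the gain costs almost nothing.

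The size rests on assumed baseline prevalence, assumed new-onset risks and the share of baseline cases who tick ringing. For 1% versus 5% at 5% prevalence, counting everyone gives 35% power if all tick and 47% to 49% if half do, against 73% in the restricted analysis. The TD and resistance-gene objectives and the sample size are not affected.

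**What to change.** Add one analysis rule before unblinding. Tinnitus as a drug effect is ringing reported during or after travel by participants who answered No to Appendix C item 3, compared by arm; alternatively, the comparison is adjusted for item 3. Participants who answered Yes are listed separately by arm. Those who answered Don't know or preferred not to answer form their own category, with a sensitivity analysis that includes them.

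The cost is a slightly smaller denominator, 2% to 10% under the prevalences assumed here. No extra data or visits are needed.

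Keep the existing ringing row, so that the raw report is preserved. A supplementary item asking whether the ringing is new or worse than before the trip is optional. It would capture worsening, but under the Study Instruments section it needs an IRB amendment. It also relies on self-judged change in a trial whose Study Limitations section concedes that dark stool and mouth discoloration may reveal the arm.
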